8.3.9.2 Unanticipated Problem Reporting

Unanticipated problems (UPs) should be reported by the investigator to the reviewing IRB and OCR.

9 STATISTICAL CONSIDERATIONS

OBJECTIVES	Hypothesis
9.2 Primary	
Determine if fecal microbial transplantation leads to clinical improvement in refractory fecal incontinence in older women.	Our working hypothesis is that the St. Mark's Vaizey score, a measure of fecal incontinence severity, will significantly improve at 4 weeks after FMT, and will be maintained at 12 weeks, relative to baseline. A secondary outcome will be quality of life at 4 and 12 weeks.
Primary Safety	
Determine the safety of FMT administration via NG tube in older women with FI.	Our hypothesis is that there will be low occurrence of serious adverse events following administration of FMT via NG tube.
Secondary	
Determine whether the effectiveness of microbial engraftment following fecal microbial transplantation is associated with the degree of clinical improvement.	Our working hypothesis is that more transplanted strains will be present at 4 weeks in subjects with a higher response score.
Tertiary	
Determine whether the baseline microbiota configuration affects engraftment in fecal microbial transplantation for fecal incontinence.	Our working hypothesis is that the transplant will be more effective in baseline samples with lower microbial diversity.

9.1 Statistical Hypotheses

9.3 Sample Size Determination

Initial open label clinical trials of FMT for irritable bowel syndrome were performed with 10-15 patients. (Holvoet, Gut 2017; Pinn ,Am J Gastro, 2014; Mazzawi, PLoS One, 2018) In the proposed pilot study, we will examine 15 evaluable women with refractory fecal incontinence to gather essential feasibility and outcomes data to conduct a future RCT of FMT. In a prior study of 13 adults with irritable bowel syndrome, significant differences in signals for several bacteria (*Bacteroides, Desulfitispora, Bifidobacteria*) were noted between 8 responders and 5 non-

responders to FMT (response rate 60%). (Mazzawi PLoS One, 2018) If the response rate is near 60% in our pilot study, we will be able to detect a difference in bacterial engraftment of 1.59 standard deviations. Our power will be decreased if the response rate is either very low (<3) or very high (>12). With 15 subjects in a single arm study, the response rate will be determined to within 10% (interquartile range).

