1 STUDY SUMMARY

1.1 Synopsis Title: Fecal Microbial Transplantation (FMT) For the Treatment of Fecal Incontinence in Women FMT for FI **Short Title:** Open label pilot study assessing FMT to treat fecal incontinence in Study women > 50 years of age. **Description: Objectives:** The primary objective is to determine if fecal microbial transplantation leads to clinical improvement in fecal incontinence. Change in the St. Mark's Vaizey score, a measure of fecal incontinence Primary severity, 4 weeks after FMT. **Endpoint:** Secondary Determine whether the effectiveness of microbial engraftment following **Endpoints:** fecal microbial transplantation is associated with the degree of clinical improvement. Determine whether the baseline microbiota configuration affects engraftment in fecal microbial transplantation for fecal incontinence. Our working hypothesis is that the transplant will be more effective in baseline samples with lower microbial diversity. 15 evaluable women, > 50 years of age, who have been diagnosed with Study **Population:** fecal incontinence and have failed standard treatment. 1/2Phase: **Description of** Penn Medicine - University of Pennsylvania Health System Sites/Facilities Participants will be enrolled form the Urogynecology clinics at the Enrolling University of Pennsylvania. **Participants: Description of** Participants will undergo fecal microbial transplantation (FMT) using the Penn Microbiome Therapy – 002 (PMT-002): no more than 152 mL Study **Intervention:** suspension for intragastric or intraduodenal administration from 40g human stool, comprising $1 \times 10^8 - 1 \times 10^{12}$ anaerobic bacterial CFUs/dose. **Study Duration:** 24 months **Participant** Approximately 8 months **Duration:**

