3 STUDY OBJECTIVES AND ENDPOINTS

OBJECTIVES	ENDPOINTS
Primary	
Determine if fecal microbial transplantation leads to clinical improvement in refractory fecal incontinence in older women.	Number of subjects that show significant improvement at 4 weeks after FMT, and will be maintained at 12 weeks, relative to baseline using the St. Mark's Vaizey score, a measure of fecal incontinence severity.
Primary Safety	
Determine the safety of FMT administration via naso-gastric tube in older women with FI.	Frequency of adverse events, serious adverse events, and adverse events of special interest (including allergic reaction and gastrointestinal symptoms).
Secondary	
Determine if FMT leads to improved quality of life for subjects.	Number of subjects that have an improved quality of life at 4 and 12 weeks, measured by the FIQL scale.
Determine if the effectiveness of microbial engraftment following fecal microbial transplantation is associated with the degree of clinical improvement.	Concentration of microbiota present at baseline vs. at week 4 and at 12 weeks (optional)in subjects that demonstrate a significant improvement at 4 weeks after FMT, relative to baseline using the St. Mark's Vaizey score.
Tertiary	
Determine whether the baseline microbiota of the subject affects engraftment in fecal microbial transplantation for fecal incontinence.	Concentration of microbiota at baseline vs. concentration of microbiota at 4 weeks and at 12 weeks (optional).

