7 STUDY INTERVENTION DISCONTINUATION AND PARTICIPANT DISCONTINUATION/WITHDRAWAL

7.1 Participant Discontinuation/Withdrawal from the Study

Participants are free to withdraw from participation in the study at any time upon request and without impact to their regular medical care, but they will receive no further treatment with this investigational product.

An investigator may discontinue or withdraw a participant from the study for the following reasons:

- Significant study intervention non-compliance.
- If any clinical adverse event (AE), laboratory abnormality, or other medical condition or situation occurs such that continued participation in the study would not be in the best interest of the participant.
- If the participant meets an exclusion criterion (either newly developed or not previously recognized) that precludes further study participation.

The reason for participant discontinuation or withdrawal from the study will be recorded on the Case Report Form (CRF). Subjects who sign the informed consent form and do not receive FMT will be replaced.

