7.2 Lost To Follow-Up

A participant will be considered lost to follow-up if they fail to return for greater than 2 scheduled visits and is unable to be contacted by the study site staff.

The following actions must be taken if a participant fails to return to the clinic for a required study visit:

• The site will attempt to contact the participant and reschedule the missed visit within 2 weeks and counsel the participant on the importance of maintaining the assigned visit schedule and ascertain if the participant wishes to and/or should continue in the study.

• Before a participant is deemed lost to follow-up, the investigator or designee will make every effort to regain contact with the participant (where possible, 3 telephone calls and, if necessary, a certified letter to the participant's last known mailing address or local equivalent methods). These contact attempts should be documented in the participant's medical record or study file.

• Should the participant continue to be unreachable, he or she will be considered to have withdrawn from the study with a primary reason of lost to follow-up.

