9.4 Statistical Analyses

9.4.1 General Approach

Data on safety outcomes will be summarized using descriptive statistics. Feasibility of conducting a clinical trial of FMT will be calculated by measuring the feasibility of conducting a clinical trial of FMT will be calculated by percentage of screened patients who enroll in the study (Number enrolled / Number screened x 100). Fecal incontinence severity symptom and quality of life (QOL) scores at baseline, 4 and 12 weeks after FMT treatment will be compared using Friedman test (repeated measures ANOVA for non-parametric data) Responder will be defined as 5 point or greater improvement in St. Mark's score from baseline to 4 weeks following FMT.

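### The efficacy set, response-rate denominator and missing-score handling are undefined, and the three-visit Friedman test discards a valid week-4 score when week 12 is missed

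*Combined protocol and SAP*

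**What the plan says.** - **Sample size.** Section 9.3 states "we will examine 15 evaluable women with refractory fecal incontinence". The synopsis uses the same adjective for its 15 women. Neither place says what makes a woman evaluable.
- **Replacement.** Section 7.1 has the only replacement rule: "Subjects who sign the informed consent form and do not receive FMT will be replaced". Nothing is said about replacing, or leaving out of the analysis, a woman who was treated and then left.
- **Responder.** Section 9.4.1: "Responder will be defined as 5 point or greater improvement in St. Mark's score from baseline to 4 weeks following FMT". This uses two visits. No denominator is given.
- **Test of the scores.** Section 9.4.1 says that severity and quality-of-life scores at baseline, "4 and 12 weeks after FMT treatment will be compared using Friedman test". No other test of the St. Mark's score is named.
- **Primary endpoint.** The synopsis gives the change in St. Mark's score 4 weeks after FMT. Section 3 gives a count: "Number of subjects that show significant improvement at 4 weeks after FMT, and will be maintained at 12 weeks".
- **Missing data.** Section 10.1.7 has missing data resolved with the investigator during monitoring. That is a query step, not an analysis rule. Section 9 has no rule.

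**The concern.** Women can leave after treatment: Section 7.1 allows free withdrawal and withdrawal by the investigator for an adverse event. A treated woman with no week-4 score cannot be classed under the responder definition, and the plan does not say whether she counts as a non-responder or drops out of the denominator. In an open-label single-arm study of 15 women, one woman is worth about 7 percentage points (1/15), and there is no control arm to offset selective loss. The rate is meant to inform a later randomized trial, so an ambiguous denominator carries forward into its planning.

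The second problem is one of efficiency. The synopsis places the primary question at week 4, but the only named test runs over three visits. In its standard form the Friedman test ranks scores within each woman across all visits and omits any woman with a gap. A woman with good baseline and week-4 scores who misses week 12 is then lost to the only formal test of the primary score.

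**Working it through.** **1. The plan's own figures.** Section 9.3 gives a detectable engraftment difference of 1.59 SD at a response rate near 60%, and a response rate known to within 10% (interquartile range).
- A two-sample t-test of 9 responders against 6 non-responders gives 1.598 SD. Two-sided alpha 0.05 and 80% power are assumed, since neither is stated.
- Half the interquartile range of the estimated rate is 0.6745 × √(0.6 × 0.4 / 15) = 0.085, or ±8.5 points.

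Both figures reproduce. The point made here does not put them in error.

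**2. Response rate under different denominators.** The inputs are 15 evaluable women (Section 9.3) and a 60% response, so 9 responders. The number D of further treated women lost before week 4 is an assumption, because the documents give no dropout figure. The rate over all treated women lies between 9/(15 + D), if none of the lost women responded, and (9 + D)/(15 + D), if all did.

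| D | Evaluable only | None of the lost responded | All of the lost responded |
|---|---|---|---|
| 1 | 9/15 = 60% | 9/16 = 56% | 10/16 = 63% |
| 2 | 9/15 = 60% | 9/17 = 53% | 11/17 = 65% |
| 3 | 9/15 = 60% | 9/18 = 50% | 12/18 = 67% |

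Exact 95% intervals: 9/15 gives 32% to 84%; 9/18 gives 26% to 74%.

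If instead 15 are treated with no top-up and two are lost, observed cases give 9/13 = 69%. The all-treated range is then 9/15 = 60% to 11/15 = 73%.

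**3. Direction.** The error from using completers only is d × (p_c − p_d), where d is the fraction of treated women lost, p_c the response rate in completers and p_d the rate the lost women would have had. With p_c = 60% and d = 20% (assumed):
- p_d = 0%: 0.20 × 0.60 = +12 points
- p_d = 30%: 0.20 × 0.30 = +6 points
- p_d = 60%: 0
- p_d = 100%: 0.20 × (−0.40) = −8 points

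The rate is overstated only if the lost women would have done worse than those who stayed. That is plausible if women leave for lack of benefit or poor tolerance, but it is not certain.

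**4. A woman who misses only week 12.** The Section 9.4.1 responder definition uses baseline and week 4, so she is still classed and the effect on that rate is zero. She does leave the Friedman test.

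**5. Cost to the test.** The simulation inputs are all assumed: normal scores, an improvement of 0.8 SD at week 4 kept at week 12, correlation 0.5 between visits, and alpha 0.05.

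| Analysis | Women used | Power |
|---|---|---|
| Friedman, all three scores present | 15 | about 73% |
| Friedman, three week-12 scores missing | 12 | about 65% |
| Paired Wilcoxon at week 4, same three missing week 12 | 15 | about 79% |

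The Friedman test loses about 8 points for data that the week-4 question does not need.

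**The case against.** A reader might infer that the plan excludes treated dropouts. It does not say so. The replacement rule in Section 7.1 covers only women who never received FMT, which fits a reading in which evaluable means treated and every treated woman counts. That stands, but even on this reading a treated woman without a week-4 score has no stated handling.

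A reader might also infer that the response rate is biased upward, or that the three-score requirement causes such a bias. Neither follows. The direction depends on outcomes that would not be observed, and the responder definition in Section 9.4.1 does not use week 12. Week 12 would enter the count only if the maintenance wording in Section 3 became part of response. The move from 60% to 50% also lies well inside the 32% to 84% interval for 9/15.

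The plan takes real steps against missing scores. Weeks 4 and 12 may be done remotely (8.1.4, 8.1.5), withdrawing women are asked to complete the next visit's assessments (8.1.7), and missed visits trigger repeated contact (7.2). The lost-to-follow-up rule, ending with "he or she will be considered to have withdrawn from the study with a primary reason of lost to follow-up", governs how a withdrawal is recorded, not who is analysed. These steps make gaps less likely but do not say how to analyse those that remain.

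Finally, this is a pilot that was not sized on the Friedman test, and the power figures rest on assumed inputs. That limits the weight of the power loss, but discarding observed week-4 scores has no offsetting benefit for a week-4 question.

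**Conclusion.** The concern holds in two limited parts.

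First, evaluable, the response-rate denominator and the handling of missing scores are undefined. The response rate may therefore be overstated. With 9 responders in 15 and three further treated dropouts, the all-treated rate could be anywhere from 50% to 67%. The low end assumes that every dropout is a non-responder, and the number of dropouts is an assumption throughout. The documents support neither a stated exclusion of treated dropouts nor a proven upward bias.

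Second, the only named test of the primary score drops any woman who misses week 12, although the synopsis endpoint is at week 4. Under the assumed effect and correlation, three such gaps take power from about 73% to 65%, against about 79% for a paired week-4 test on all 15. This part concerns the test only, not the responder rate.

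Both should be settled before results are seen, since the study is unblinded.

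**What to change.** Add two statements to Section 9.4.1:

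1. The week-4 change in St. Mark's score is tested by a paired analysis (for example the Wilcoxon signed-rank test) in every woman with baseline and week-4 scores, whether or not week 12 is available. The three-visit comparison is supportive.
2. The response rate is reported over all women who received any PMT-002, with a missing week-4 score counted as non-response. Observed-case and best-case results (missing counted as response) are shown as sensitivity analyses.

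The term evaluable in the synopsis and Section 9.3 should then be defined to agree with this. If the maintenance wording in Section 3 is meant to be part of response, a matching rule for a missing week-12 score is needed.

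The cost is a few sentences, with no new data or visits. The headline response rate may be slightly less favourable. Counting missing as non-response is a conservative assumption that can understate the rate, which is why the other two results should stand beside it.

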9.4 Statistical Analyses

9.4.1 General Approach

Data on safety outcomes will be summarized using descriptive statistics. Feasibility of conducting a clinical trial of FMT will be calculated by measuring the feasibility of conducting a clinical trial of FMT will be calculated by percentage of screened patients who enroll in the study (Number enrolled / Number screened x 100). Fecal incontinence severity symptom and quality of life (QOL) scores at baseline, 4 and 12 weeks after FMT treatment will be compared using Friedman test (repeated measures ANOVA for non-parametric data) Responder will be defined as 5 point or greater improvement in St. Mark's score from baseline to 4 weeks following FMT.

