5 STUDY POPULATION

5.1 Inclusion Criteria

• Women \geq 50 years of age with self-reported fecal incontinence defined as:

- uncontrolled bothersome loss of liquid or solid fecal material that occurs at least weekly over the last 3 months **and**

- failure of response to conservative management using fiber, diet modification, supervised pelvic floor exercises

- Baseline St. Mark's score of ≥ 12
- Intolerance, unwillingness, or inadequate response to constipating medications
- Self-reported current negative colon cancer screening based on the 2016 US preventive Services Task Force recommendation (applies to participants age 50-75). N/A if participant is over 75
- Able and willing to sign the informed consent form and agree with study procedures

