8.1.5 Visit 3 (12 weeks post treatment)

Participants will return to the office for visit 3, twelve weeks (\pm 7 days) after the FMT treatment. The clinical research coordinator will collect final one-week BM diary as well as the stool sample (if available). This visit may occur via telemedicine or telephone, and samples provided via mail or drop off at the clinical site. The following questionnaires will be completed:

- Medication Log
- Adaption Index
- PFIQ-7
- SF-12
- PFDI-20
- ABLe Questionnaire
- FIQL
- Bristol Stool Index
- St. Mark's Score
- PGSC
- Global Impression Improvement
- PACSYM
- AE/SAEs

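### The primary endpoint is stated in two incompatible ways, and the only efficacy test, a three-visit Friedman test with no follow-up contrast, does not by itself answer the two-part hypothesis

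*Combined protocol and SAP*

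**What the plan says.** Section 1.1 (Synopsis) gives the primary endpoint as "Change in the St. Mark's Vaizey score, a measure of fecal incontinence" severity, measured 4 weeks after FMT. Section 3 gives it as "Number of subjects that show significant improvement at 4 weeks after FMT, and will be maintained at 12 weeks, relative to baseline", again on the St. Mark's score. The hypothesis under 9.2 returns to the score and says that it "will significantly improve at 4 weeks after FMT, and will be maintained at 12 weeks, relative to baseline".

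Section 9.4.1 holds the efficacy analysis. Severity and quality-of-life "scores at baseline, 4 and 12 weeks after FMT treatment will be compared using Friedman test". It adds that "Responder will be defined as 5 point or greater improvement" in St. Mark's score, counted from baseline to week 4. It names no pairwise comparison, estimate of change, interval or significance level.

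Section 9.3 plans 15 evaluable women and says that "the response rate will be determined to within 10% (interquartile range"). It gives no power or precision figure for the score. Entry under section 5.1 requires "Baseline St. Mark's score of" 12 or more.

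**The concern.** Two current sections name different primary results. One is a change in score at a single visit; the other is a number of women and adds a condition at week 12. A reader of the final report could not tell which result the trial was set up to deliver.

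Neither version is matched by the named test. The hypothesis has two parts: the score is better at week 4, and it is still better at week 12. A three-visit Friedman test asks only whether the three visits share one distribution. Rejection does not say which visit differs, in which direction, or whether an early gain lasted. No contrast follows to say so.

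The week-12 condition in section 3 also has no numeric rule, so that count needs a decision the plan has not made. Section 6.3 says neither subjects nor investigators are blinded, so such a decision could be taken with results in view. The study exists to supply outcomes data for a later randomised trial, which needs a defined endpoint and an estimate of change more than an omnibus p-value.

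**Working it through.** **1. The plan's own figures.** None concerns the score or the Friedman test.
- Detectable engraftment difference, 1.59 SD: at 60% response, 15 × 0.6 = 9 responders against 6 non-responders. A two-sample t calculation (two-sided 5% and 80% power, neither stated) gives 1.598 SD. It reproduces, but concerns engraftment.
- Response-rate precision: standard error = √(0.6 × 0.4 / 15) = 0.1265; quartile half-width = 0.6745 × 0.1265 = 0.085. This agrees with the stated 10%. The exact 95% interval for 9 of 15 is 32% to 84%.

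**2. The Friedman test cannot tell the patterns apart.** This step assumes no effect size or correlation. The statistic is 12 / [nk(k+1)] × ΣR² − 3n(k+1), where R is a visit's rank sum, n = 15 and k = 3. So 12/180 = 0.0667 and 3 × 15 × 4 = 180. Take 15 women in whom one visit stands clear of the other two, and those two differ trivially, 8 women one way and 7 the other.
- Gain at week 4 kept at week 12: baseline ranks highest in every woman. Rank sums are 45, 22 and 23. ΣR² = 2025 + 484 + 529 = 3038.
- Gain at week 4 wholly lost: week 4 ranks lowest in every woman. Rank sums are 15, 37 and 38. ΣR² = 225 + 1369 + 1444 = 3038.
- Gain at week 12 only: week 12 ranks lowest, so again 15, 37 and 38.
- Worsening at week 4 only: week 4 ranks highest, so again 45, 22 and 23.

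All four give 3038 × 0.0667 − 180 = 22.53 and, on 2 degrees of freedom, p = exp(−22.53/2) = 0.000013.

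**3. How often this would matter.** Simulation, 20,000 trials per pattern. From the plan: n = 15 and entry at 12 or more. Assumed: SD 4, unselected mean 16, integer scores held to 0-24, equal correlation between visits, two-sided 5%, 3-point effect. Percent of trials rejecting at correlation 0.3 / 0.6 / 0.8:

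| True pattern | Friedman | Paired signed-rank |
|---|---|---|
| Gain kept at week 12 | 79 / 91 / 99 | week 12: 84 / 92-94 / 99 |
| Gain wholly lost by week 12 | 69 / 86-87 / 99 | week 12: 8 / 6-7 / 6 |
| Change at week 12 only | 68 / 86 / 99 | week 4: 6 to 8 |
| 3 points fading to 1.5 | 65 / 81 / 97 | week 4: 83 / 94 / 99; both visits: 37 / 47 / 66 |

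At correlation 0.6, Friedman for kept against lost is 98 v 98 with SD 3 and 81 v 72 with SD 5; the paired week-12 test is 99 v 5 and 85 v 8. Repeats with fewer trials moved the figures checked by no more than 3 points. In this model the entry rule alone yields an apparent gain of about 0.7 / 0.4 / 0.2 points.

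**The case against.** **The week-12 clause in section 3 may be hypothesis text carried into the endpoint cell.** It matches the 9.2 sentence closely, and both the synopsis and the responder rule fix week 4. This has force. The 5-point rule plausibly supplies the meaning of significant improvement, so a week-4 responder count can be worked out. It remains true that one section names a score and another a count, and no sentence links the 5-point rule to the endpoint.

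**Any omnibus test behaves like this, and the visit means can be read beside it.** Largely so. In the same model, among trials where Friedman rejected, the observed week-12 gain was at least half the week-4 gain in 97-99.8% of trials if the effect was kept and in 1-12% if it was lost. A fading effect was not classified (56-63%). Section 9.4.1 promises descriptive summaries explicitly only for safety.

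**A reader might infer that the reported count could swing widely with the meaning of maintained.** With assumed true gains of 6 points at week 4 and 4 at week 12 and correlation 0.6, cut-offs of 5, 3 and 1 points at week 12 give 40%, 56% and 65%, or about 6, 8 and 10 of 15. The documents do not support that spread as a finding. The gains are invented, the 3- and 1-point cut-offs appear nowhere in the plan, and its only threshold is 5 points.

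**A reader might also infer serious loss of data.** A standard Friedman test drops a woman who has no week-12 score even if her week-4 score is valid. But missed visits are rescheduled (7.2), the week-4 visit may be remote (8.1.4), and for week 12, "This visit may occur via telemedicine or telephone". Women who withdraw are asked to complete the next visit's activities (8.1.7). No dropout figure is given, so this is only a minor added reason.

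**It is a 15-woman open-label pilot with no power claim for the score.** True, and it limits the weight of the point. It does not remove the contradiction.

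**Conclusion.** The concern holds as a specification fault that should be fixed. Sections 1.1 and 3 contradict each other on the primary endpoint. The one named efficacy test does not, by itself, show week-4 improvement or week-12 persistence. The identical statistics in step 2 establish the second point without any assumed effect. The size, about 91% against 87% for Friedman where a paired week-12 test gives 92-94% against 6-7%, rests on the assumed SD of 4, correlation of 0.6 and 3-point effect. At correlation 0.3 the Friedman gap is wider, 79% against 69%, but still far from a usable distinction.

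The documents do not support saying that the trial cannot describe durability at all, that the week-4 responder count is indeterminate, or that the result is likely to be distorted by missing week-12 scores.

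**What to change.** Reconcile sections 1.1, 3 and 9 to one primary endpoint; the choice is the sponsor's.

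- **If the score is chosen:** make the primary analysis a paired baseline-to-week-4 signed-rank test with a Hodges-Lehmann estimate and 95% interval, on all women with both scores. Test baseline to week 12 at the same two-sided 5% level only if week 4 is significant (fixed sequence).
- **If the count is chosen:** make the primary analysis the week-4 responder proportion (5 points or more) with an exact 95% interval, and the paired score tests secondary.
- **In either case:** state that significant improvement means the 5-point rule. Report the maintained-responder proportion with an exact interval under a week-12 rule fixed before analysis, for example the plan's own 5 points applied at week 12. Keep Friedman as supportive. State that change after entry at 12 or more includes regression to the mean.

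The cost is wording in three sections and two named contrasts on data already collected. The omnibus test is no longer the headline. Requiring significance at both visits has less power than Friedman: about 88% against 91% if the effect is kept, and 47% against 81% if it fades (correlation 0.6). The paired test is also slightly more exposed to regression to the mean. With no true effect and correlation 0.6, it rejects 11% against 10% for Friedman if the unselected mean is 14, and 23% against 20% if it is 12. No single-arm test removes that.
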